7.4. Data Sources

[figure not shown]
EHRs provide real-world clinical data with broad patient populations and have been increasingly used for post-approval drug safety studies over the past two decades in Europe and North America. In China, there are three major types of electronic healthcare databases including population-based EHR, electronic medical records (EMRs), and national claims. Since 2014, via collaboration with academic institutions in China, Pfizer has been evaluating these data sources and has determined that they provide potential value to post-marketing drug safety studies, particularly population-based EHRs. Yinzhou EHR database is selected for this study because this population-based EHR database consists of complete immunization records and healthcare data of all children in the district.

7.4.1. Yinzhou EHR Database

Yinzhou is one of the largest districts of economically developed Ningbo city in Zhejiang province, China and consists of approximately 1.6 million populations (740,000 permanent residents and 860,000 temporary residents). The Yinzhou EHRs include data from three main sources (Figure 2):

- Yinzhou CDC databases;
- Healthcare data including EMRs, claims and e-prescriptions from hospitals and community health centers within the district;
- Healthcare data including EMRs, claims and e-prescriptions from the Women and Children's hospital of Ningbo city.

Figure 2. Components of Yinzhou EHR Database

Data from these data sources are entered into Yinzhou EHR database in real time. These data sources are linked via each individual's unique personal identification number (termed the national identification (NID) number) used by each resident throughout life in China. In a situation where children do not yet have a NID number, data of those children are matched by names of children, dates of birth, names of parents/legal guardians, or home addresses.

Yinzhou CDC database: There are two CDC databases (ie, Immunization Administration Registry and CDC AEFIS) in the district. The Immunization Administration Registry includes immunization data at CDC immunization clinics for both type I and type II vaccines for all children aged <7 years. The AEFIS is a passive surveillance system and collects AEFIs reports. All cases reported to AEFIS are to be investigated, with the exception of common adverse reactions that have a clear diagnosis (eg, fever, redness, and swelling on the injection site; induration).

Healthcare data from hospitals and community health centers within the district:

Yinzhou district collect healthcare data of its residents from hospitals (3 tertiary general hospitals and 1 specialized hospital) and community health centers (20) within the district including inpatient and outpatient visits from all hospitals and outpatient visits from all community health centers within the district.

Healthcare data from the Women and Children's Hospital of Ningbo city: The Women and Children's Hospital of Ningbo city is the only children hospital in the city. It is essential to have data from this hospital being part of Yinzhou EHR database because this hospital is very likely to be the hospital of choice if families would seek medical care for their children outside hospitals of Yinzhou district.

7.4.2. Evaluation of Yinzhou EHR Database

Yang et al conducted a detailed assessment of characteristics of Yinzhou EHR database in 2016 and concluded that Yinzhou database has the necessary attributes for post-marketing drug safety surveillance and pharmacoepidemiologic studies, ¹⁰ however, the data quality and its suitability for a post-approval vaccine safety study among pediatric populations was not assessed previously. It was therefore essential to conduct a pilot study before moving forward with a full-scale study using Yinzhou EHR database. Therefore, Pfizer, collaborating with Fudan University and Yinzhou CDC, performed a pilot study to further evaluate the Yinzhou EHR database from September to December 2017. Preliminary results of the pilot study indicated that the Yinzhou EHR database can be used to fulfill the requirement of this PAC, despite some limitations identified at the pilot study such as sub-classifications of some ICD codes used in the database are either omitted and/or combined with a few related or unelated diagnoses and a large number of children from transient families (temporary residents) move in or out of the district within a short period of time. To address these limitations, a validation study will be conducted.

7.5. Validation Study

To minimize potential biased estimates in the main study, a validation study will be conducted. This validation study consists of two parts: validation of ICD codes used to identify all SOIs in the main study and a prospective cohort study in a sub-population of the main study.

7.5.1. Validation of ICD Codes

To evaluate the accuracy of the ICD-10 codes or ICD-10 codes based algorithm for identifying all SOIs in the main study, relevant medical records of children having the ICD codes for these events are going to be obtained from hospitals within Yinzhou district and Women and Children's hospital of Ningbo city and outpatient medical records from community health centers within the district by Yinzhou CDC. A data abstraction form will be used to abstract data from the medical records. The abstracted data will be sent to an adjudication committee to determine whether the identified case is a true case. Then the adjudicated outcomes will be entered to the validation study database for analyses. The Positive Predicted Value (PPV) of the ICD code or ICD code algorithms will be calculated for the SOIs, using an adjudicated safety outcome based on the medical record as the gold

standard. Although this study will attempt to obtain all relevant medical records of all children having the ICD codes from these hospitals and community health centers, it is possible that some medical records of these children may not be available for various reasons. Procedures for this component are shown on Figure 3.

7.5.2. A Prospective Cohort Study in a Sub-Population

A prospective cohort study in a sub-population of the main study was initiated on 1 August 2018 after obtaining the approval of Human Genetic Resources Administration of China (HGRAC) application. The prospective cohort study will end on 31 July 2020. Potential participants are enrolled at the time of a visit to CDC immunization clinics after the informed consent is obtained. An initial questionnaire for the first dose is administered to parents/legal guardians of children in the office by healthcare professionals (HCPs) at the immunization clinics when a child receives the 13vPnC vaccination. A follow-up questionnaire at 7 days post-vaccination is administered by the HCPs either via a telephone or face-to-face interview to parents/legal guardians of the children. The initial questionnaires and follow-up questionnaire are completed for each dose of the 13vPnC vaccination. It should be noted that responsibilities of HCPs at the CDC immunization clinics are to administer vaccines to children and they are not children's treating HCPs.

Both a web-based questionnaire and a paper-based questionnaire are made available to the HCPs for their preference. The HCPs at CDC immunization clinics have access to the web-based questionnaire via their work computers. Based on the feedback from Yinzhou CDC, the HCPs would be likely to use the web-based questionnaire for a face-to-face interview and a paper-based questionnaire for a phone interview. However, if a paper questionnaire is used at an interview, the HCP will be instructed to transfer the data from the completed paper questionnaire by completing a web-based questionnaire. A copy of the completed paper questionnaire will be uploaded to the validation study database. It is expected that completion of the initial questionnaire and the follow-up questionnaire will take approximately 20 minutes and 15 minutes respectively.

The questionnaires are pretested on a sample of HCPs and parents/legal guardians and revised to ensure clarity. Data elements on the questionnaire are similar to that in the main study based on Yinzhou EHR database including: demographic information; household characteristics; medical history; and occurrences of the SOIs. Questions on the questionnaires consist of both yes/no and multiple-choice answers. For questions related to SOIs, information on the date of onset, visits to a healthcare facility, the doctor's diagnosis, etc. is collected. The questionnaires do not solicit adverse events (AEs) other than the SOIs. There are no open-ended questions. Any product safety information that is otherwise volunteered will be handled in the manner described in the Section 9.3.

In addition, a child's medical records will be abstracted by Yinzhou CDC and reviewed by the adjudication committee if the parent/guardian indicates that the child visits a healthcare facility for one of the SOIs. The adjudicated outcomes will be subsequently entered and stored in the validation study database that is housed by Wanda Inc, the database builder and manager of Yinzhou EHR database. Although this study will attempt to obtain all relevant medical records of all children indicated a visit to a healthcare facility for the SOIs, it is

possible that some medical records of these children may not be available for various reasons. Procedures for this prospective cohort study are shown on Figure 3.

[figure not shown]

Figure 3. Procedures for the Validation Study

7.6. Study Size

This study includes all children 1 to 24 months of age who have received at least one dose of 13vPnC in the Yinzhou EHR database. Although the number of children in the Yinzhou EHR database varies from year to year, the birth rate in Yinzhou district has been steady with approximately 8,000 live-births each year. The coverage for the 7vPnC dose 1 vaccine in China was approximately 10% for children under 24 months. Assuming the same coverage for the 13vPnC dose 1 in Yinzhou district, the study size was originally estimated to be 3,200 children exposed to at least one dose of 13vPnC during the approximately three-year study period. However, as of 30 January 2019, approximately 10,000 children 1 to 24 months of age in the Yinzhou EHR database have already received at least one dose of 13vPnC since the start of the main study (ie, 1 May 2017). Based on the newly available data, the study size is now re-estimated to be approximately 22,000 for the approximately three-year study period.

7.7. Data Management

All data for the main study are collected through the routine data collection practices of the Yinzhou EHR database. The data in the Yinzhou EHR database are updated continually. The principal investigator or his delegates at Fudan University will have access to de-identified study specific data generated by the data builder and manager of the Yinzhou EHR database (Wanda Inc) via a secure server. Data for the main study will be stored in the form of SAS® datasets at the secure server.

Data obtained from the validation study will also be housed and managed by Wanda Inc. Fudan University and Pfizer have full access to the de-identified study database. Although identifiable data such as children's NID numbers, their dates of birth, their names, etc. will be collected in one part of the validation study (ie, the prospective cohort study in a sub-population of the main study), these identifiable data will only be used by Wanda Inc to link children who participate in both the main study and the validation study for the purpose of analyses. The identifiable data will not be shared with Fudan University, Pfizer, or other third parties.

The first annual progress report to NMPA presented the study status since the HGRAC application for the study was pending. To prepare the subsequent annual progress reports to NMPA, the main study database is to be queried to identify the number of eligible children who have received a 13vPnC vaccination. For these children, routinely collected data are abstracted for the study variables: demographics; medical history; coadministration of other type I and type II vaccines if any, and the SOIs. Counts of the study variables in the main study will be included in the 2019 progress report and descriptive analyses will be conducted for the 2020 progress report.

Eligible children are followed in the Yinzhou EHR from the date of the first dose of the 13vPnC vaccination until 7 days after the last dose of the 13vPnC vaccination, moving out of the district, death, loss to follow-up, or the end of the study (whichever occurs first) for the occurrence of the SOIs.

All data will be maintained by a trained group of data managers from Wanda Inc ensuring compliance with national regulations in China. SAS® will be used for the statistical analyses.

7.8. Data Analysis

All analyses for the study will be descriptive. The descriptive analyses will include frequency distributions of age at the time receiving each dose of 13vPnC, gender, residential status, year of 13vPnC vaccinations, co-administration of other vaccines at the same date, and medical history. In addition, frequency distributions of the number of SOIs by age, gender, residential status, season of diagnosis, hospitalization, and year of 13vPnC vaccinations will also be described. The frequency distributions mentioned above will be tabulated for both the main study and the prospective cohort study in the sub-population of the main study.

Incidence rates per 1,000 person-days at risk and per 1,000 doses and its 95% CIs of the SOIs will be calculated in three different time periods (ie, 0-3 days, 4-7 days, and 0-7 days post-vaccination) by all doses and by each dose. Additional analyses (eg, stratification by gender, residency, and co-administration of other vaccines) will be performed. The incident rates will be estimated for both the main study and the prospective cohort study in the sub-population of the main study.

The percentage of children's medical charts that are available for the validation study will be described. The PPV of an ICD-10 code or ICD-10 code based algorithm used to identify the SOIs against adjudicated SOIs based on the information from medical records of children as a gold standard will be calculated for the validation of these codes in the main study. Additionally, the PPV of a reported SOI by parents/legal guardians that requires medical attentions against the adjudicated SOI based on the information from medical records of children as a gold standard will be also calculated in the prospective cohort study in the sub-population of the main study. Finally, among children who participate in both the main study and the prospective cohort study, sensitivity and specificity of an ICD code or ICD-10 code based algorithm identifying seizures or apnea in the main study will be calculated using the adjudicated seizures or apnea in the prospective cohort as a reference standard (ie, a gold standard). A positive percent of agreement and a negative percent of agreement will be estimated between an ICD code or ICD-10 code based algorithm identifying fever or urticaria and angioedema in the main study and the reported fever or urticaria and angioedema by parents/legal guardians in the prospective cohort as a non-reference standard (ie, a non-gold standard).

Additional exploratory analyses and sensitivity analyses may be conducted. Detailed methodology for summary and statistical analyses of data collected in this study will be documented in a SAP, which will be dated, filed and maintained by the sponsor. The SAP may modify the plans outlined in the protocol; any major modifications of endpoint definitions or their analyses would be reflected in a protocol amendment.

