7. RESEARCH METHODS

7.1. Study Design

This is an observational study based on a population-based EHR database. In addition, a validation study including validation of International classification of diseases, tenth revision (ICD-10) codes or ICD-10 code based algorithm for identifying all SOIs and a prospective cohort study in a sub-population of the main study will be conducted in order to offset the potential biased results from the main study because of potential misclassification of the SOIs due to miscoding and/or undercoding of ICD-10 codes used to identify the SOIs in the EHR database.

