Nevertheless, there are several limitations to this study. First, one main potential source of confounding is co-administration of multiple vaccines. Although co-administration of type I and type II vaccines is not recommended by China CDC, it exists in practice. Additionally, it is possible that other type II vaccines may be administrated simultaneously with 13vPnC. For example, Hib, Pentaxim, RV1, and IPV vaccines can be given at the same time as 13vPnC in Children aged 2 months and 4 months based on China CDC recommended vaccine schedule. It may not be possible to differentiate safety outcomes of these vaccines although there is a plan to conduct analyses to estimate the incidence rates of the safety outcomes for those receiving 13vPnC only and for those receiving 13vPnC plus co-administration of other vaccines (Section 7.8). Second, it is possible that some children may receive medical care from hospitals outside of the catchment area. This information will not be captured by Yinzhou EHR except the care under Women and Children's hospital of Ningbo city. However, it is reasonable to assume that the vast majority of families are likely to go to the Women and Children's hospital of Ningbo city for the care since the next nearest Children's hospital is about two hour away while the Women and Children's hospital of Ningbo is less than a half hour away. Third, similar to any studies using secondary data sources, misclassification of SOIs may exist, since Yinzhou EHR is not designed for the research purpose. SOIs not requiring medical attentions tend to be systematically undercoded (eg, low fever and mild urticaria and angioedema) in these data sources. Although the prospective cohort study in a sub-population of the main study will be able to ascertain some of these events not requiring medical attention, it is possible that a small percentage of the events may be still under-reported. Fourth, like the rest of China, it is expected that a small percentage (approximately 10%) of children from families with sufficient financial resources may receive 13vPnC in Yinzhou district, It is possible that children receiving 13vPnC may be from tails of the target children population on either ends that may not be the same as the rest of the target population in terms of health status. As a result, the incidence of safety outcomes of interest in the study may be either substantially lower or higher than that in countries that 13vPnC is included in the national childhood immunization programs or covered by private insurance. Furthermore, SOIs requiring treatment may be miscoded. But, the validation study will allow evaluation of the magnitude of misclassification as well as provide more accurate estimation of the incidence rates of SOIs. Last, some children in Yinzhou EHR don't have a NID number during the study period. Healthcare data of these children will be mapped based on a combination of dates of birth, names of children, names of parents/legal guardians, or home addresses in the EHR

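### The validation study is meant to offset or minimise misclassification bias in the main study, but section 7.8 carries none of its results into a main-study incidence rate

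*Protocol*

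**What the plan says.** Three places in the protocol state what the validation study is for.

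- Section 7.1: its two parts, code validation and a prospective cohort, are done "in order to offset the potential biased results from the main study because of potential misclassification of the SOIs".
- Section 7.5: "To minimize potential biased estimates in the main study, a validation study will be conducted".
- Section 7.11: "the validation study will allow evaluation of the magnitude of misclassification as well as provide more accurate estimation of the incidence rates of SOIs".

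Section 7.8 lists the analyses. On incidence: "The incident rates will be estimated for both the main study and the prospective cohort study in the sub-population of the main study". On validation, it plans the share of charts available and the PPV of the codes, with the adjudicated record as "gold standard will be calculated for the validation of these codes in the main study". It also plans the PPV of parent-reported events. Among children in both studies, "sensitivity and specificity of an ICD code or ICD-10 code based algorithm identifying seizures or apnea in the main study will be calculated". Fever, and urticaria and angioedema, get positive and negative percent agreement with parent report, which the section calls a non-gold standard.

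Section 7.8 adds that exploratory and sensitivity analyses may follow and that detailed methods go to the SAP.

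**The concern.** Sections 7.1 and 7.5 speak of the main study's own results. A PPV or a sensitivity printed beside a rate describes the bias in that rate but does not reduce it. The main-study rates are the first objective in section 6, and the study is a post-authorisation commitment to the regulator, so these figures are likely to be quoted.

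The protocol gives reasons for error in both directions. Section 7.4.2 reports that some code sub-classifications are missing or merged with other diagnoses, some of them unrelated, which makes false positives plausible. Section 7.11 says that "SOIs not requiring medical attentions tend to be systematically undercoded", which means missed events. A reader given only a raw rate and a PPV might multiply the two, and would then correct one error and leave the other.

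**Working it through.** **1. Purpose against named analysis.** The protocol gives no PPV, sensitivity or event rate, so there is no figure of its own to reproduce. The check is of the text.

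- Section 7.3: main-study outcomes are identified by ICD coding, except that events from the passive reporting system (AEFIS) are text diagnoses.
- Section 7.5.1: coded cases are adjudicated and the results go into the validation study database. All charts are to be sought: "Although this study will attempt to obtain all relevant medical records of all children having the ICD codes", some may not be available.
- Section 7.7: main-study data come from routine collection in the health-record database.
- Section 7.8: rates are planned for the main study and for the cohort. No main-study rate is restricted to adjudicated cases, weighted by PPV or divided by sensitivity.

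The protocol therefore plans the ingredients of a correction but names no main-study rate that uses them.

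**2. What a correction could do (illustration only).** Let C be the coded count, T the true count and Se the sensitivity. True positives equal both C × PPV and T × Se, so

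T = C × PPV / Se, and C / T = Se / PPV.

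The confirmed-case count is C × PPV = T × Se. It removes false positives only and cannot exceed T. It lies further from T than the raw count does when T − C × PPV > C − T, that is, when Se < 2 PPV / (1 + PPV).

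For the interval of a PPV-weighted rate, take the log-scale variance of the count as 1/C. With a share f of charts available, that of the PPV is (1 − PPV) / (PPV × f × C). The ratio of interval widths is √[1 + (1 − PPV) / (PPV × f)], and C cancels. Here f = 0.8 is assumed.

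| Assumed PPV | C/T at Se 0.5 | C/T at Se 0.9 | Se below which confirmed-only is further from T | Interval width ratio |
|---|---|---|---|---|
| 0.5 | 1.00 | 1.80 | 0.667 | 1.50 |
| 0.7 | 0.71 | 1.29 | 0.824 | 1.24 |
| 0.9 | 0.56 | 1.00 | 0.947 | 1.07 |

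Example: with C = 100, PPV 0.7 and Se 0.5, T = 100 × 0.7 / 0.5 = 140. The raw count is 40 too low, and the confirmed count of 70 is 70 too low. A confirmed-case rate must therefore stand beside the code-based rate and not replace it.

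**3. Reach of the cohort rates.** Section 7.2.1 admits to the cohort only consented children with a first dose from 1 August 2018. Section 7.6 gives about 10,000 children by 30 January 2019 and 22,000 expected in all. From 1 May 2017 there are 457 days to 31 July 2018 and 640 to 30 January 2019. Under even accrual to that date, 10,000 × 457/640 = 7,141 children started too early, or 32% of 22,000. If the accrual rate instead rises linearly to reach 22,000 at day 1,181, the figure is about 6,700 (30%). This describes coverage of the cohort rates. It is not an error in any rate.

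**The case against.** The strongest reply has four parts.

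*The cohort is the remedy.* It is half of the validation study, its rates are a formal objective, and section 7.11 names it as the means of picking up events that need no medical care. This largely stands for section 7.11, whose promise of more accurate rates is not tied to the main study. A reader might infer that this promise is broken; the text does not support that. The reply is weaker for section 7.1 and does not answer section 7.5, which refers to estimates in the main study.

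*This belongs in the SAP.* The SAP may well contain a correction, and weighting, intervals and the treatment of AEFIS events do belong there. But section 7.8 itself sets out the validation analyses measure by measure, so the use to which they are put can be named there too. It also reserves major changes to endpoint definitions or their analyses for a protocol amendment, and a rate on adjudicated events arguably comes close to that.

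*The rates are not purely code-based.* A reader might infer that they are. AEFIS events are recorded as text, so that reading goes too far. What holds is that no adjudicated main-study rate is named.

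*The remedy is partial and the study is descriptive.* A confirmed-case rate cannot mend undercoding, and the planned measures will make misclassification visible anyway. Both points are correct. They limit the weight of the concern and explain why the added rate should be a supplement, but the mismatch between purpose and analysis remains.

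**Conclusion.** The point holds as a gap between a stated purpose and the analyses named. Sections 7.1 and 7.5 say that the validation will offset or minimise bias in the main-study results, whereas section 7.8 only measures that bias.

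The protocol does not show how large the bias is or which way it runs. The range of 0.56 to 1.80 rests wholly on an assumed PPV and sensitivity of 50% to 90%, and should not be read as an estimate for this database. Nor does the protocol show that no correction will be made, since the SAP was not seen. The change is worth making because it is cheap and the main-study rates are the first objective.

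**What to change.** In section 7.8, state that:

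- main-study incidence rates for each safety outcome will also be reported for adjudication-confirmed cases, beside the code-based rates, with missing charts, confidence intervals and AEFIS events handled as set out in the SAP;
- for seizures and apnea, if event numbers allow, a rate corrected for both errors (coded rate × PPV / sensitivity) will be shown;
- the confirmed-case rate removes false positives only, can understate incidence where events are undercoded, and supplements the code-based rate;
- for fever, and for urticaria and angioedema, the reader is referred to the cohort rates on undercoding.

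The cost is a few sentences and some programming, since charts for all coded children are already to be sought and adjudicated. There are three downsides. Intervals widen (1.07 to 1.50 times under the assumptions above). Charts must be assumed missing at random. Sensitivity from the cohort must be assumed to apply to the whole main study, although under section 7.5.2 cohort charts are reviewed only when a parent reports a healthcare visit, so it refers to medically attended events.

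If no corrected rate is to be reported, reword sections 7.1 and 7.5 to say that the validation quantifies misclassification in the main study. That costs two sentences.

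### Positive agreement of the EHR codes with all parent-reported fever and urticaria/angioedema, read alone, cannot separate missed coding from events that never reached care; a split by healthcare visit would do much of this with data already planned

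*Protocol*

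**What the plan says.** Section 7.8 assigns a code-validation measure to each safety outcome of interest (SOI).

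- **Seizures and apnea:** sensitivity and specificity of the code against the adjudicated outcome in the prospective cohort.
- **Fever and urticaria/angioedema:** positive and negative percent agreement between the code and "the reported fever or urticaria and angioedema by parents/legal guardians in the prospective cohort as a non-reference standard". The comparison is not limited to events for which care was sought.
- **All SOIs:** a positive predictive value (PPV) of the code against adjudicated charts, and "the PPV of a reported SOI by parents/legal guardians that requires medical attentions against the adjudicated SOI". The second PPV is limited to attended events, but it does not involve the code.

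Section 7.1 gives miscoding and undercoding of ICD-10 codes as the reason for the validation study. Section 7.11 describes two mechanisms. The first is that "SOIs not requiring medical attentions tend to be systematically undercoded (eg, low fever and mild urticaria and angioedema) in these data sources". The second is that "SOIs requiring treatment may be miscoded. But, the validation study will allow evaluation of the magnitude of misclassification".

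Section 7.5.2 says the questionnaire collects "information on the date of onset, visits to a healthcare facility" and the doctor's diagnosis for the SOIs. It also says charts are abstracted and "reviewed by the adjudication committee if the parent/guardian indicates that the child visits a healthcare facility for one of the SOIs". Section 7.7 provides for linking children who are in both the main study and the cohort.

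**The concern.** An event for which no care was sought can rarely carry a diagnosis code. When the comparator is every parent-reported event, disagreement has two main sources: the family did not seek care, or the child was seen and the code was not recorded. The planned positive agreement pools them.

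The two sources mean different things to a reader of the Objective 1 rates. Non-attendance limits any EHR-based study. Missed coding among attended children points to the code list or algorithm, which can be examined and revised. Section 7.4.2 makes the second a live possibility: the pilot found ICD sub-classifications left out or merged with other diagnoses, and the validation study is named as the response.

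The two PPVs do not fill the gap. The code PPV starts from coded events, so it finds false positives and not misses. The parent-report PPV compares the report with the chart and says nothing about the code. For these two SOIs, no named measure shows how many attended events go uncoded.

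**Working it through.** The protocol states no agreement figure, care-seeking rate or coding rate, so there is no planned figure to reproduce. All values below are assumptions used to show the structure.

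**Identity.** Let *a* be the share of parent-reported events with a visit captured in the EHR, *s* the share of those that carry the code, and *u* the share of the remaining events that are nevertheless identified. Parent reports are taken as correct.

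Positive agreement = *a* × *s* + (1 − *a*) × *u*

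If unattended events are never coded, *u* = 0 and this becomes *a* × *s*.

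**One number, two unknowns (*u* = 0).** For an observed agreement of 0.20, *s* = 0.20/*a*:

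| *a* | *s* |
|---|---|
| 0.20 | 1.00 |
| 0.30 | 0.67 |
| 0.50 | 0.40 |
| 0.80 | 0.25 |
| 1.00 | 0.20 |

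The same result fits perfect coding or 20% coding.

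**Ceiling (*u* = 0).** With perfect coding, *s* = 1 and agreement equals *a*. If 5% to 40% of reported events reach care, agreement cannot exceed 0.05 to 0.40.

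**Effect of a split by visit.** Assume 200 reported events, with exact (Clopper-Pearson) 95% intervals.

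| | Case A | Case B |
|---|---|---|
| Attended | 0.20 × 200 = 40 | 0.60 × 200 = 120 |
| Coded | 0.9 × 40 = 36 | 0.3 × 120 = 36 |
| Pooled agreement | 36/200 = 0.18 (0.129–0.240) | 36/200 = 0.18 (0.129–0.240) |
| With a visit | 36/40 = 0.90 (0.763–0.972) | 36/120 = 0.30 (0.220–0.390) |
| Without a visit | 0/160 (0–0.023) | 0/80 (0–0.045) |

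The pooled figures are identical and the intervals with a visit do not overlap. With 50 reports, pooled agreement is 9/50 = 0.18 (0.086–0.314) in both cases. The split gives 9/10 (0.555–0.997) against 9/30 (0.147–0.494), still separate but wide.

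**If *u* is not zero.** With *u* = 0.05:

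- Case A: 0.18 + 0.80 × 0.05 = 0.22
- Case B: 0.18 + 0.40 × 0.05 = 0.20

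The ceiling softens, but the pooled figures remain close while *s* is 0.90 in one case and 0.30 in the other.

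**What the split still mixes.** A reported visit may have taken place outside the EHR catchment. If the 4 uncoded visits in case A were all outside it, coding within the EHR would be 36/(40 − 4) = 36/36, not 36/40. This is why such visits need to be counted separately.

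**The case against.** **The planned measure fits the objective and is honestly labelled.** Objective 1 concerns the incidence of SOIs, not of medically attended SOIs. For that purpose total under-capture is relevant whatever its cause, and Section 7.8 calls the parent report a non-gold standard. This stands: the measure should be kept. A reader might infer that the comparator is wrong or mislabelled, and the text does not support that.

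**A further table row is ordinary SAP content.** Section 7.8 allows additional exploratory and sensitivity analyses and lets the SAP modify the plan. This stands in part. Nothing prevents the addition, so the plan is not locked. But Section 7.8 does choose the comparator and the measures, and Section 7.11 relies on the validation study to show the size of misclassification.

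**Planned outputs might nearly recover the split.** If unattended events are never coded, every event in the agreement numerator was attended, and the denominator of the parent-report PPV approximates the attended reports. This works only if counts are given per SOI and nearly all charts are found. So *cannot separate* applies to the agreement figure read alone, not to everything the study will hold.

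**The ceiling is not exact.** Section 7.3 also draws outcomes from text diagnoses in the passive adverse-event system. Whether these enter the comparison is unclear, and if they do, an unattended event could be identified. The ceiling is therefore approximate.

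**Code PPV already addresses miscoding.** It does so for wrongly assigned codes. Attended but uncoded events remain unmeasured for two of the four SOIs.

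**The split does not isolate coding failure.** Out-of-catchment visits and missing charts remain. This is correct, and the fix asks for both to be counted.

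**Conclusion.** The point holds as an inexpensive improvement. Read alone, positive agreement for fever and urticaria/angioedema mixes non-attendance or non-capture with missed coding, and no named measure shows the attended events that the codes miss. The validation result for these two SOIs is therefore less informative about undercoding than Sections 7.1 and 7.11 suggest.

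The size depends on care-seeking and coding rates that the protocol does not give. The algebra assumes that parent reports are correct and that unattended events are seldom coded. Within those limits, one pooled value such as 0.18 is compatible with code capture among attended events anywhere from 0.18 (all attended) to 1.00 (18% attended).

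Two stronger inferences are not supported. First, a reader might conclude that the incidence rates are miscalculated; no Objective 1 or 2 rate changes, only how the validation result is interpreted. Second, a reader might take "in order to offset the potential biased results from the main study because of potential misclassification of the SOIs" in Section 7.1, or the matching statement in Section 7.5, as a promise to correct the main-study rates that the analysis then breaks. The cohort rates under Objective 2 are a coherent parallel estimate, and supplying them is a fair reading of that language.

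**What to change.** In Section 7.8, for fever and for urticaria/angioedema:

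1. Keep overall positive and negative percent agreement with parent report, as a measure of total under-capture.
2. Add positive agreement separately for reported events with and without a healthcare visit, using the existing questionnaire item. Negative agreement stays overall, because doses without a reported event have no visit to split on.
3. Within the visit group, give the share of chart-adjudicated events that carry the code, using the charts already sought under Section 7.5.2.
4. Report the number of unavailable charts and, where the chart shows it, the number of visits outside the EHR catchment, since those reflect non-capture and not miscoding.

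The cost is a few table rows and no new collection. The downsides are smaller denominators, wider intervals (for example 0.555–0.997 for 9 of 10) and dependence on a visit item reported by parents.
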